#### **e. Reporting and Exclusions**

Missing data will not be imputed or carried forward in any of the analyses.

The sample size for continuous variables will be the number of subjects with non-missing data; in the summary of categorical variables, subjects with missing data will be excluded in the calculation of percentages.

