#### 4. PATIENT POPULATION

**a. Enrollment Goal**

This study aims to enroll 80 subjects. With an anticipated acceptance rate of 2/3, this means we will approach 120 eligible candidates over that period. We estimate we will be able to achieve 30-day follow-up in 80% of enrolled patients.

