#### **5.2.6 30 DAY POST DISCHARGE/WITHDRAWAL FOLLOW-UP**

Subjects will receive a follow-up phone call from a study coordinator and Medical Charts will be reviewed to assess if the subject was readmitted within 30 days of discharge. Follow-up phone call and Medical Chart review will instead occur 30 days after withdrawal for patients who are withdrawn prior to discharge.

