#### **d. Analysis of Secondary Endpoints**

Time (in days) in between PRN treatments, change in respiratory inspiratory flow rate from baseline to discharge, length of stay, at-home drug compliance, 30-day readmissions (all-cause and COPD/Asthma exacerbation), and 30-day survival will be compared between patients who were and were not readmitted using t-tests or chi-square tests (or Wilcoxon Rank Sum tests and Fisher's Exact tests), as appropriate.

The efficacy of the treatment protocol in the study cohort compared to the historical cohort will be assessed by comparing (1) the average number of PRN treatments per patient day while hospitalized estimated using a robust Poisson regression model (2) length of stay in the hospital, and (3) the rate of rehospitalization, using the Wilcoxon Rank sum test.

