## **9.2 Informed Consent**

The investigator or delegated person must explain to each subject the nature of the study, its purpose, the procedures involved and any discomfort it may entail. Each subject must be informed that participation in the study is voluntary, that he/she may withdraw from the study at any time, and that withdrawal of consent will not affect his/her subsequent medical treatment or relationship with the treating physician.

The informed consent should be given by means of a standard written statement, written in nontechnical language. The subject should read and consider the statement before signing and dating it and should be given a copy of the signed document. No subject can enter the study before his/her informed consent has been obtained. The ICF must be submitted by the Investigator for IRB approval.

There will also be an option to do electronic consenting and electronic signatures by using study approved methods such as hospital telehealth system, patient iPad, telephone calls/telephone video conferencing. Documents will be sent electronically to the email address you provide for you to review the documents and sign off on.

A telephone call will be made by an authorized study research staff member to assess if the subject was readmitted within 30 days of discharge.

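### 30-day survival has no stated data source, and excluding missing subjects lets unseen deaths drop out; the rule for combining call and chart for readmission is also missing

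*Combined protocol and SAP*

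**What the plan says.** Section 2.d and Section 8.7.a list 30-day survival and 30-day readmission among the endpoints. Section 8.7.d says that "30-day readmissions (all-cause and COPD/Asthma exacerbation), and 30-day survival will be compared" between patients who were and were not readmitted. Section 8.7.c uses the same split for the primary endpoint, the count and rate of PRN treatments.

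The day-30 data come from Section 5.2.6: "Subjects will receive a follow-up phone call from a study coordinator and Medical Charts will be reviewed to assess if the subject was readmitted". The window is the 30 days after the patient leaves hospital. Section 9.2 repeats the purpose of the call: "A telephone call will be made by an authorized study research staff member to assess if the subject was readmitted within 30 days of discharge". Section 8.2 adds one further use of the call, home drug compliance. None of these sections mentions vital status. The Synopsis lists it under safety assessments, without a source or a time point. The text below Table 1 in Section 6.1 limits adverse-event and serious-adverse-event reporting to the period from enrollment to discharge.

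On completeness, Section 4.a says: "We estimate we will be able to achieve 30-day follow-up in 80% of enrolled patients". On missing data, Section 8.7.e rules out imputation and adds that "in the summary of categorical variables, subjects with missing data will be excluded in the calculation of percentages".

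**The concern.** A subject who has died cannot answer the call. If the death happened at home or in another hospital, the site chart may not show it. The plan describes no alternate contact, no search of death records and no request for outside records, and safety reporting has already closed. Under Section 8.7.e such a subject is missing and leaves the denominator. Whether a subject is missing then depends partly on the outcome being measured, and dropping missing subjects does not protect against that.

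For readmission the gap is different. Two sources are named, but no rule covers a subject who is not reached and whose chart shows nothing. That subject might be missing or might count as not readmitted. The choice affects the readmission rate and also who falls in each group in Sections 8.7.c and 8.7.d. An unseen death counted as not readmitted would sit in the more favourable group.

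**Working it through.** **Inputs from the documents.** Section 4.a: "This study aims to enroll 80 subjects" and "With an anticipated acceptance rate of 2/3, this means we will approach 120 eligible candidates over that period". The plan's own figure reproduces: 80 / (2/3) = 120. Expected follow-up is 80 × 0.80 = 64, leaving 16. The documents give no expected death rate, no readmission rate and no share of readmissions that return to the same system. Those values below are assumptions.

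**Survival.** Assume 4 deaths among 80, a true mortality of 4/80 = 5.0%. Let m be the deaths among the 16 without follow-up that nobody sees. Reported mortality is (4 − m)/64:

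- m = 0: 4/64 = 6.3%
- m = 1: 3/64 = 4.7%
- m = 2: 2/64 = 3.1%
- m = 4: 0/64 = 0%

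With 8 deaths (10%), the figures are 12.5% if none is missed, 6.3% if half are and 0% if all are. The exclusion rule is neutral only when the unseen share of deaths equals the share of subjects excluded, here 16/80 = 20%. Above that share, survival is overstated; below it, survival is understated.

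**Survival bounds without assumptions on the missing.** If none of the 64 followed dies, mortality over 80 lies between 0/80 = 0% and 16/80 = 20%.

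**Readmission.** Assume a true rate of 20% in reached and unreached alike, with 70% of the unreached patients' readmissions visible in the system's charts.

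- Events seen: 64 × 0.20 + 16 × 0.20 × 0.70 = 12.8 + 2.24 = 15.04.
- Unreached subjects with clean charts excluded: 15.04 / (64 + 2.24) = 22.7%.
- Unreached subjects with clean charts counted as not readmitted: 15.04 / 80 = 18.8%.
- All 16 unreached excluded, whatever the chart shows: 12.8 / 64 = 20.0%. If the unreached have 1.5 times the overall risk (30%), this becomes (16 − 4.8) / 64 = 17.5%.

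Varying the visible share from 50% to 90% gives 22.0% to 23.4% under the first rule and 18.0% to 19.6% under the second.

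**Readmission bounds.** If 13 of the 64 followed are readmitted (20.3%), the bounds over 80 are 13/80 = 16.3% and 29/80 = 36.3%.

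**The case against.** Several stronger readings are tempting, and the documents do not support them.

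- A reader might infer that readmissions found in charts enter the rate while the corresponding non-events are lost. Section 5.2.6 provides for chart review of subjects generally and can be read as classifying everyone. A clean chart would then mean not readmitted, and the error would be under-counting of outside admissions. Excluding clean charts is one possible reading only.
- A reader might infer that survival must be biased towards 100%. It need not be. If every death is found while living subjects are lost, mortality is overstated (6.3% against 5.0% above). If all four deaths fall among the unreached and all are visible, survival is 64/68 = 94.1%, below the true 95%.
- A reader might take the 80% as the share reached by telephone. Section 4.a speaks only of 30-day follow-up. If that means call or chart, the 16 are subjects with neither source, and the readmission calculation above, which relies on charts for those 16, does not apply as set out.
- A reader might infer that the primary result is compromised. The descriptive summary of PRN treatments uses in-hospital data only. Only the readmitted versus not-readmitted comparison depends on day-30 status, and no effect on it has been calculated.

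The readmission errors shown (+2.7 and −1.2 points) are also smaller than the standard error of the comparison with the 60 historical charts. At 20% that is about √(0.2 × 0.8 × (1/60 + 1/67.2)) = 7.1 points, where 67.2 = 64 + 16 × 0.20 is the study denominator if charts show every readmission among the unreached.

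These objections limit the claim about direction and size. They leave the missing source for vital status, the missing combination rule and the exclusion rule untouched.

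**Conclusion.** The point holds in this form: 30-day survival is an endpoint with no stated source, and the exclusion rule lets deaths outside the system disappear from it. Survival may be overstated, and overstatement is the likelier direction because a dead subject cannot answer a call, but the direction is not fixed. With 4 assumed deaths in 80, reported mortality ranges from 0% to 6.3% against a true 5%. With no observed deaths among 64, values up to 20% cannot be excluded.

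For readmission, the plan leaves open a choice that moves an assumed 20% to 22.7% or 18.8%. That is modest against sampling error, but it is systematic and avoidable, and it also defines the groups in Sections 8.7.c and 8.7.d. All event rates and the in-system share are assumptions. The counts of 64 and 16 take the Section 4.a estimate at face value.

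**What to change.** 1. Amend Section 5.2.6 to collect an alternate contact at enrollment and to record vital status and readmission at day 30 for every treated patient, from the subject, the alternate contact or the chart.
2. State that all-cause readmission is classified from either source for everyone, and that a subject is missing only when neither source is informative.
3. For these two endpoints, replace the Section 8.7.e exclusion rule with reporting over all treated patients. Count in-hospital deaths as events for survival, and show the number with unknown status and best-case and worst-case bounds.
4. Use chart-verified readmission only for the comparison with the 60-chart historical cohort, so that both sides are ascertained alike.
5. Report deaths without readmission as a separate category, and add a sensitivity analysis of the Section 8.7.c comparison that leaves them out of the not-readmitted group.

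Two simpler remedies should be avoided. Limiting the headline readmission rate to the site's own system would redefine the all-cause endpoint and, at a 70% in-system share for all patients, would report 0.20 × 0.70 = 14% against a true 20%. Making readmitted-or-died the main grouping would set known survival to 100% in the other group, which empties the survival comparison in Section 8.7.d.

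The cost is one extra field at enrollment, a few more calls, some added wording in the analysis section and possibly a less favourable survival figure.

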## **9 ETHICS AND GOOD CLINICAL PRACTICE**

### **9.1 Institutional Review Board/Independent Ethics Committee**

The Investigator will submit this protocol and ICF for IRB approval prior to starting the study. The Investigator will not begin any study subject activities until approval from the IRB has been documented and provided as a letter to the Investigator. Before implementation, the Investigators will submit to and receive documented approval from the IRB of any modifications made to the protocol or any accompanying material to be provided to the subject

after initial IRB approval, except for those necessary to reduce immediate risk to study subjects.

## **9.2 Informed Consent**

The investigator or delegated person must explain to each subject the nature of the study, its purpose, the procedures involved and any discomfort it may entail. Each subject must be informed that participation in the study is voluntary, that he/she may withdraw from the study at any time, and that withdrawal of consent will not affect his/her subsequent medical treatment or relationship with the treating physician.

The informed consent should be given by means of a standard written statement, written in nontechnical language. The subject should read and consider the statement before signing and dating it and should be given a copy of the signed document. No subject can enter the study before his/her informed consent has been obtained. The ICF must be submitted by the Investigator for IRB approval.

There will also be an option to do electronic consenting and electronic signatures by using study approved methods such as hospital telehealth system, patient iPad, telephone calls/telephone video conferencing. Documents will be sent electronically to the email address you provide for you to review the documents and sign off on.

A telephone call will be made by an authorized study research staff member to assess if the subject was readmitted within 30 days of discharge.

## **9.3 Declaration of Helsinki**

The Investigator must conduct the study in accordance with the principles of the current version of the Declaration of Helsinki. Copies of the Declaration of Helsinki and

amendments will be provided upon request or can be accessed via the website of the World Medical Association at <http://www.wma.net/en/30publications/10policies/b3/index.html>

## 10. COMPENSATION

Participants will not receive any compensation for participating in this study.

## 11. COSTS

Participants will not incur any additional costs due to study participation. Patient or their insurance company will be required to pay for all expenses related to regular care including hospital care.

## 12. SAFETY MONITORING

Safety will be assessed by monitoring the following:

- Vital signs,
- height,
- body weight,
- concomitant medication use,
- AEs, SAEs,
- Pregnancy testing for women of childbearing potential, as determined by the study PI

## 13. DATA SAFETY MONITORING COMMITTEE (DSMC)

It has been determined that this study does not need a DSMB as the study drug has full FDA approval.

## 14. RISK AND BENEFITS TO PARTICIPANTS

## 14.1 POTENTIAL BENEFITS

There may or maynot be be any direct benefit to the patients who participate in this study.

## 14.2 POTENTIAL RISKS

### 14.2.1 Drug Adverse events

- COPD: Most common adverse reactions (incidence  $\geq 1\%$ ) are upper respiratory tract infection, pneumonia, bronchitis, oral candidiasis, headache, back pain, arthralgia, influenza, sinusitis, pharyngitis, rhinitis, dysgeusia, constipation, urinary tract infection, diarrhea, gastroenteritis, oropharyngeal pain, cough, and dysphonia. (6.1)
- Asthma: Most common adverse reactions (incidence  $\geq 2\%$ ) are pharyngitis/nasopharyngitis, upper respiratory tract infection/viral upper respiratory tract infection, bronchitis, respiratory tract infection/viral respiratory tract infection, sinusitis/acute sinusitis, urinary tract infection, rhinitis, influenza, headache, and back pain. (6.2)

### 14.2.2 Physical Risks

The Ellipta oral inahler may cause a bad taste, soreness or irritation of the mouth and throat.

### 14.2.3 Psychosocial & Privacy Risks

Any time information is collected there is a potential for loss of confidentiality. Every effort will be made to keep participant's information confidential, however this cannot be guaranteed.

Participation in research study may make participants feel uncomfortable.

Participants will be informed that they may refuse to participate or stop their participation at any time without effect on future medical treatment or relationship with the treating physician.

#### 14.2.4 Reproductive Risks and Contraception Guidelines

Women must meet the non-productive potential definition below to be eligible.

Non-reproductive potential is defined as:

➤ *Pre-menopausal females with one of the following:*

- Documented tubal ligation.
- Documented hysteroscopic tubal occlusion procedure with follow-up confirmation of bilateral tubal ligation.
- Hysterectomy
- Documented Bilateral Oophorectomy

➤ *Postmenopausal defined as:*

12 months of spontaneous amenorrhea with an appropriate clinical profile (e.g., age appropriate, >45 years, in the absence of hormone replacement therapy). In questionable cases for women <60 years of age, a blood sample with simultaneous follicle stimulating hormone and estradiol falling into the central laboratory's postmenopausal reference range is confirmatory. Females under 60 years of age, who are on HRT and whose menopausal status is in doubt, are required to use a highly effective method to avoid pregnancy if they wish to continue their HRT during the study. Otherwise, they must discontinue HRT to allow confirmation of postmenopausal status prior to study enrolment. For most forms of HRT, at least 2 to 4 weeks will elapse between the cessation of therapy and the blood draw; this interval depends on the type and dosage of HRT. Following confirmation of their post-menopausal status, subjects can resume use of HRT during the study without use of a highly effective method to avoid pregnancy.

### 15. RISK/BENEFIT ASSESSMENT

There may be no direct benefit to the subjects. However, the information obtained may help to advance the understanding of COPD disease and improve treatment protocols, may thus be of future benefit to patients with these disorders or to at-risk members-of-society. The subjects incur

no cost from participating in this study. They are also not paid for their participation. As, except for the study drug, all other medical care will be part of routine care, they are still responsible for the costs of the hospitalization, clinic visit, and any clinical labs ordered by their doctors.

## 16. Protocol amendment procedures and data retention

### 16.1 PROTOCOL AMENDMENTS AND OTHER CHANGES IN STUDY CONDUCT

#### Protocol Amendments

Any substantive changes will be made as formal amendments to the protocol and will be submitted for appropriate review by an institutional review board (IRB), and to regulatory authorities.

Any change or addition to this protocol requires a written protocol amendment that must be approved by GlaxoSmithKline plc. (GSK) and the Investigator before implementation.

Amendments affecting the safety of subjects, the scope of the investigation, or the scientific quality of the study require additional approval by the IRB. Examples of amendments requiring such approval are:

1. A significant change in the study design (e.g., addition or deletion of a control group)
2. An increase in the number of invasive procedures to which subjects are exposed
3. Addition or deletion of a test procedure for safety monitoring

These requirements for approval should in no way prevent any immediate action from being taken by the Investigator to ensure the safety of all subjects included in the study. If an immediate change to the protocol is deemed necessary by the Investigator and is implemented by him/her for safety reasons, GlaxoSmithKline plc. (GSK) should be notified, and the IRB should be informed within 10 working days.

Protocol changes affecting only administrative aspects of the study do not require formal protocol amendments or IRB approval, but the IRB must be kept informed of such administrative changes.

## 16.2 RECORDING OF DATA, DOCUMENTATION, AND RETENTION OF DOCUMENTS

Data will be stored and evaluated in such a way as to guarantee subject confidentiality in accordance with the legal stipulations applying to confidentiality of data. All study records must be available for inspection by the Sponsor, its authorized representatives, the FDA, and other regulatory authorities.

Data on subjects collected on CRFs during the study will be documented in an anonymous fashion and the subject will only be identified by the study number and by initials if also required. If, as an exception, it is necessary for safety or regulatory reasons to identify the subject, both Gilead Sciences, Inc. and the Investigator are bound to keep this information confidential.

The Investigator must maintain source documents for each subject in the study, consisting of all demographic and medical information, and must keep a copy of the signed ICF. The subject's clinical source documents (usually defined by the project in advance to record key efficacy/safety parameters independent of the CRFs) would include but are not limited to the subject's hospital/clinic records, physicians' and nurses' notes, appointment book, original laboratory reports, ECG, pathology, and special assessment reports and signed ICFs. All information on the CRFs must be traceable to these source documents in the subject's file. Data without a written or electronic record will be defined before study start and will be recorded directly on the CRFs, which will be documented as being the source data.

Essential documents defined in the ICH Guidance on Good Clinical Practice (ICH E6) and listed below, must be retained by the Investigator for as long as needed to comply with national and international regulations. The Sponsor will notify the Investigator(s)/institution(s) when the study-related records are no longer required. The Investigator agrees to adhere to the document retention procedures by signing the protocol.

Essential documents include:

1. IRB approvals for the study protocol and all amendments
2. All source documents and laboratory records
3. CRF copies
4. Subjects' ICFs (with study number and title of study)
5. Country-specific regulatory documents

### 16.3 Auditing Procedures

Investigator understands that source documents for this study must be made available to appropriately qualified personnel from the Sponsor or its designees, to the IRB, and/or to health authority inspectors after appropriate notification. The verification of the CRF data must be by direct inspection of source documents. The Sponsor conducts audits of clinical research activities in accordance with internal SOPs to evaluate compliance with the principles of GCP. A regulatory authority may also wish to conduct an inspection (during the study or even after its completion). If an inspection is requested by a regulatory authority, the Investigator must immediately inform the Sponsor that this request has been made.

### 17. Publication of Results

An integrated clinical and statistical report will be prepared at the completion of the treatment period. However, it is intended that the results of the study will be included on <http://clinicaltrials.gov> and published and/or presented at scientific meetings.

All personnel that are involved with this protocol or that will have access to the Biobank have passed the IRB certifying examination. The personnel will only include faculty and staff employed at the recruitment site (BUMC).

